6.8. Intervention After the End of the Study

This is a healthy volunteer study and no follow-up intervention is planned.

7. DISCONTINUATION OF STUDY DRUG AND SUBJECT DISCONTINUATION/WITHDRAWAL

7.1. Discontinuation of Study Drug

Subjects who experience a severe reaction during study drug administration resulting in interruption without completion of the administration should undergo all scheduled safety, immunogenicity, PK, and PD evaluations required by the protocol (refer to Schedule of Activities, Table 1 and Table 2). Subjects will be instructed to present for all scheduled visits and undergo all procedures per protocol.

7.2. Subject Discontinuation/Withdrawal From the Study

A subject may withdraw from the study at any time at his/her own request, or may be withdrawn at any time at the discretion of the Investigator for safety, behavioral, compliance, or administrative reasons.

- If the subject withdraws consent for disclosure of future information, the Sponsor may retain and continue to use any data collected before such a withdrawal of consent.
- Data to be collected at the time of study discontinuation and follow-up and for any further evaluations that need to be completed are specified in the Schedule of Activities (Table 1 and Table 2).

7.3. Lost to Follow-up

A subject will be considered lost to follow-up if he or she repeatedly fails to return for scheduled visits and is unable to be contacted by the study site.

The following actions must be taken if a subject fails to return to the clinic for a required study visit:

- The site must attempt to contact the subject, reschedule the missed visit as soon as possible, counsel the subject about the importance of maintaining the assigned visit schedule, and ascertain whether or not the subject wishes to and/or should continue in the study.
- Before a subject is deemed lost to follow-up, the Investigator or designee must make every effort to regain contact with the subject (where possible, 3 telephone calls and, if necessary, a certified letter to the subject's last known mailing address or similar methods). These contact attempts must be documented in the subject's medical record.
- Should the subject continue to be unreachable, he/she will be considered to have withdrawn from the study.

8. STUDY ASSESSMENTS AND PROCEDURES

All screening evaluations must be completed and reviewed to confirm that potential subjects meet all eligibility criteria. The Investigator or qualified designee will maintain a screening log to record details of all subjects screened and to confirm eligibility or record reasons for screening failure, as applicable.

8.1. Efficacy Assessments

No efficacy assessments will be obtained during this study.

8.2. Safety Assessments

Planned time points for all safety assessments are presented in the Schedule of Activities (Table 1 and Table 2).

8.2.1. Physical Examination

Each examination will include the following assessments: general appearance; skin; head, ears, eyes, nose, and throat; neck; lymph nodes; chest; heart; abdominal cavity; limbs; central nervous system; and musculoskeletal system. Height and weight (screening only) will also be measured and recorded. Body mass index will be calculated and recorded at screening.

8.2.2. Vital Signs

Vital sign measurements will be taken after the subject has been resting in the supine or semi-recumbent position for at least 5 minutes and will include temperature (°C; oral), respiratory rate, supine blood pressure, and pulse. The timing of vital sign measurements is described in the Schedule of Activities (Table 1 and Table 2). Out of range blood pressure or heart rate measurements will be repeated at the Investigator's discretion. Confirmed, clinically significant vital sign measurements will be recorded as AEs.

8.2.3. Electrocardiograms

A triplicate 12-lead ECG will be obtained after the subject has been resting for at least 5 minutes. The timing of ECGs is described in the Schedule of Activities (Table 1 and Table 2). At each time point at which triplicate ECGs are required, 3 individual ECG tracings should be obtained as closely as possible in succession, but no more than 2 minutes apart. The full set of triplicates should be completed in less than 4 minutes, 30 seconds. In addition, continuous cardiac registration will be performed in Cohorts 2, 3, and 4 as specified in Table 1.

8.2.4. Laboratory Assessments

All protocol-required laboratory assessments, as defined in Section 10.2 (Appendix 2), must be conducted in accordance with the Schedule of Activities and the laboratory manual. Clinical and laboratory assessments will be performed by a local laboratory to assess safety of ravulizumab.

• The Investigator must review the laboratory report, document this review, and record all clinically relevant changes occurring during the study in the AE section of the electronic case report form (eCRF). The laboratory reports must be filed with the source documents.

- All laboratory tests with values considered clinically significantly abnormal during participation in the study will be repeated until the values return to normal or baseline or are no longer considered clinically significant by the Investigator or medical monitor.
 - If such values do not return to normal/baseline within a period of time judged reasonable by the Investigator, the etiology should be identified and the Sponsor notified.
 - If laboratory values from non-protocol-specified laboratory assessments performed at the institution's local laboratory require a change in subject management or are considered clinically significant by the Investigator (eg, SAE or AE or dose modification), then the results must be recorded in the eCRF.
- The maximum amount of blood to be collected from each subject over the duration of the study, including any extra assessments that may be required, will not exceed 500 mL. Repeat or unscheduled samples may be obtained for safety and/or eligibility reasons or if there are any technical issues with the samples.

8.2.4.1. Virus Serology

Blood samples collected at screening will be analyzed for HIV-1, HIV-2, HBsAg, and hepatitis C virus antibody titers.

Hepatitis B surface antigen testing is required for all subjects prior to enrollment. Subjects with positive HBsAg will not be enrolled.

8.2.4.2. Vaccine Titer

A titer against meningococcal serogroups A, C, W135, and Y will be performed at screening (Schedule of Activities [Table 1 and Table 2]). Titer measurements will be used to exclude subjects without a confirmed immune response.

8.2.4.3. Immunogenicity Assessments

Antibodies to ravulizumab will be evaluated in serum samples collected from all subjects according to the Schedule of Activities (Table 1 and Table 2).

Serum samples will be screened for antibodies that bind to ravulizumab and the titer of confirmed positive samples will be reported. The detection and characterization of antibodies to ravulizumab will be performed using a validated assay method by or under the supervision of the Sponsor. Samples may be banked for a period of up to 5 years in order to perform additional safety assessments, as necessary.

Detailed instructions on the procedure for collecting, processing, storing, and shipping serum samples for immunogenicity analysis will be provided in the laboratory manual.

8.2.5. Drug and Alcohol Screen

A urine sample for drug screen will be analyzed for the substances listed in Section 10.2 (Appendix 2). Timing of urine drug and alcohol breath tests is specified in the Schedule of Activities (Table 1 and Table 2).

8.2.6. Pregnancy Testing

Pregnancy testing will be performed for all female subjects at the time points specified in the Schedule of Activities (Table 1 and Table 2).

8.2.7. Tuberculosis Testing

Serum samples for a QuantiFERON-TB test will be obtained at the time points specified in the Schedule of Activities (Table 1 and Table 2).

8.2.8. Injection or Infusion-Site Evaluation

Subcutaneous injection or IV infusion-site evaluations will be performed at the time points specified in the Schedule of Activities (Table 1 and Table 2). Injection site reactions (eg, indurations ≤ 1 cm in size) will not be listed as an AE unless they persist for more than 24 hours.

8.2.9. Vaccine and Antibiotic Prophylaxis

To mitigate the risk of *N meningitidis* infection associated with terminal complement inhibition, subjects in this study will be administered the following:

- 1. A MCV4 vaccination at least 56 days prior to dosing of ravulizumab on Day 1 (if not vaccinated with MCV4 within the last 3 years, or if subjects have been previously vaccinated but there is not adequate documentation to verify prior vaccination).
- 2. Two injections of the serogroup B meningococcal vaccine. The first injection must be administered at least 56 days prior to dosing on Day 1, with a booster administered at least 28 days prior to dosing on Day 1, with at least 28 days between the first and second injections.
- 3. Prophylactic antibiotic treatment, oral penicillin V 500 mg twice daily (equivalent to 1×10^6 units) until complement activity has normalized (as determined by CH50 assay).

The first dose of antibiotic will be administered orally on Day -1 in the evening, prior to the Day 1 (dose administration) of study drug. For the outpatient portion of the study, subjects will be instructed to take the antibiotic approximately at the same times (twice daily) on each scheduled day. A suitable system (such as text messaging) will be used for daily monitoring of subjects' compliance with the antibiotic prophylaxis regimen.

The following observations support the administration of antibiotic prophylaxis in this single-dose study:

- 1. Penicillin is the drug of choice in eradication of *N meningitidis* in carriers.
- 2. Complement-deficient patients who received monthly injections with benzathine penicillin G as prophylaxis for recurrent meningococcal disease during a 2- to 4-year period experienced significantly fewer episodes of *Neisseria* infection than deficient individuals not receiving prophylaxis (Figueroa, 1991).

- 3. High levels of resistance to penicillin caused by plasmid-encoded β -lactamases are rarely encountered in meningococcal strains (Yazdankhah, 2004).
- 4. Antibiotic prophylaxis with orally administered penicillin V 500 mg twice daily has been provided in the treatment of PNH and aHUS patients with eculizumab by some physicians and is generally well-tolerated (Kelly, 2011; Leeds Teaching Hospitals NHS Trust, 2013).

8.2.10. Risk of Infection Reminders

Risk of infection will be explained and discussed with subjects during the informed consent process, occurring at the screening visit. In order to increase the risk awareness and promote quick disclosure of any potential signs or symptoms of infection experienced by the subjects during the course of the study, additional discussion and explanation of the potential risks, signs, and symptoms, as described in the ICF, will take place at specific time points throughout the study as noted in the Schedule of Activities (Table 1 and Table 2). Subjects will also be provided a safety card to carry with them at all times.

8.3. Adverse Events and Serious Adverse Events

The definitions of an AE or SAE and specific reporting requirements are located in Section 10.3 (Appendix 3). Adverse events will be reported to the Investigator or qualified designee by the subject (or, when appropriate, by a caregiver, surrogate, or the subject's legally authorized representative).

The Investigator and any qualified designees are responsible for detecting, documenting, and recording events that meet the definition of an AE or SAE and remain responsible for following up AEs that are serious, considered related to the study drug or study procedures, or that caused the subject to discontinue the study drug (see Section 7).

8.3.1. Time Period and Frequency for Collecting Adverse Event and Serious Adverse Event Information

All AEs and SAEs will be collected from the signing of the ICF until the last follow-up visit.

Medical occurrences that begin before the start of study drug and after obtaining informed consent will be recorded on the eCRF, and will be considered as medical history.

All SAEs will be recorded and reported to the Sponsor or designee within 24 hours, as indicated in Section 10.3 (Appendix 3). The Investigator will submit updated SAE data to the Sponsor within 24 hours of the data being available.

Investigators are not obligated to actively seek AEs or SAEs after the conclusion of study participation (ie, after Day 200).

The method of recording, evaluating, and assessing causality of AEs and SAEs and the procedures for completing and transmitting SAE reports to Sponsor are provided in Section 10.3 (Appendix 3).

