^d Signed and dated EC-approved ICF must be obtained before any study-specific screening procedures are performed.

^e For subjects who do not have adequate documentation of prior MCV4 immunization or serogroup B vaccination, MCV4 immunization will be performed at least 56 days prior to dosing on Day 1, and vaccination for serogroup B meningococcal infections will be administered at least 56 days prior to Day 1 dosing with a booster administered at least 28 days prior to dosing on Day 1.

^f For subjects with a documented vaccine titer within 6 months prior to screening, the titer does not need to be repeated.

^g Complement activity, confirmed by a suitable assay such as CAP ELISA/C5 (hemolysis) inhibition, will be performed at screening to confirm subjects do not have a complement deficiency.

^h Serum pregnancy test for all female subjects of childbearing potential to confirm that a female subject is not pregnant prior to dosing.

ⁱ On Day 1, triplicate 12-lead ECGs will be performed predose and approximately 15 minutes after the EOI (Cohorts 1 through 4 only).

^j Continuous cardiac registration predose and until 3 hours after the SC injection (Cohorts 2, 3, and 4).

^k Planned randomization for Cohorts 1, 2, 3, and 5 may be up to 7 days prior to dosing on Day 1.

¹ Injection site evaluations will be performed within 15 minutes after EOI and ± 15 minutes of the other scheduled times on Day 1.

^m The Investigator or qualified designee will meet with the subject at each visit to discuss the potential safety risks of ravulizumab, and to address any safety concerns of the subject.

ⁿ Collection of adverse events and serious adverse events will begin after ICF signing.

° Subjects will be administered prophylactic antibiotic treatment, oral penicillin V 500 mg twice daily (equivalent to 1 × 106 units), beginning on the evening of Day -

1 through Day 200, or until complement activity has normalized (as determined by CH50 assay).

Protocol

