Complement	The results of each test must be entered into the eCRF.Complement activationCH50Total and free C5productorCH50Total and free C5		Total and free C5
Activity	products		

Table 9: Protocol-Required Safety Laboratory Assessments

10.3. Appendix 3: Adverse Events: Definitions and Procedures for Recording, Evaluating, Follow-up, and Reporting

Adverse Event Definition

- An AE is any untoward medical occurrence in a patient or clinical study subject, temporally associated with the use of study drug, whether or not considered related to the study drug.
- NOTE: An AE can therefore be any unfavorable and unintended sign (including an abnormal laboratory finding), symptom, or disease (new or exacerbated) temporally associated with the use of study drug.

Events Meeting the Adverse Event Definition

- Any abnormal laboratory test results (hematology, clinical chemistry, or urinalysis) or other safety assessments (eg, ECG, radiological scans, vital signs measurements), including those that worsen from baseline, considered clinically significant in the medical and scientific judgment of the Investigator (ie, not related to progression of underlying disease).
- New conditions detected or diagnosed after study drug administration even though it may have been present before the start of the study.
- Signs, symptoms, or the clinical sequelae of a suspected drug-drug interaction.

Events NOT Meeting the Adverse Event Definition

- Medical or surgical procedure (eg, endoscopy, appendectomy): the condition that leads to the procedure is the AE.
- Situations in which an untoward medical occurrence did not occur (social and/or convenience admission to a hospital).
- Anticipated day-to-day fluctuations of pre-existing disease(s) or condition(s) present or detected at the start of the study that do not worsen.

Serious Adverse Event Definition

If an event is not an AE per definition above, then it cannot be a SAE even if serious conditions are met (eg, hospitalization for signs/symptoms of the disease under study, death due to progression of disease).

A serious adverse event is defined as any untoward medical occurrence that, at any dose: 1. Results in death

2. Is life-threatening

The term 'life-threatening' in the definition of 'serious' refers to an event in which the subject was at risk of death at the time of the event. It does not refer to an event, which hypothetically might have caused death, if it were more severe.

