4.12.1 Adverse Events

A Treatment Emergent Adverse Event (TEAE) is any adverse event that commences after the start of administration of study drug.

The incidence of TEAEs (after dosing) will be summarized using the safety population. The MedDRA dictionary Version 21.0 (or higher) will be used to classify all AEs reported during the study by System Organ Class (SOC) and Preferred Term. A summary of TEAEs including the incidence of subjects who experienced TEAEs (number and percentage of subjects) and incidence of TEAEs (number of events) will be presented for each treatment group and overall, by severity and by relationship to study drug.

TEAEs and serious TEAEs will be summarized by SOC and Preferred Term for each treatment group and overall, and by relationship to study drug.

Subjects having multiple AEs within a category (e.g., overall, SOC and Preferred Term) will be counted once in that category. For severity tables, a subject's most severe event within a category will be counted. For relationship tables, a subject's event with greatest relationship to study drug within a category will be counted. In each table, SOC and Preferred Term will be presented in descending order of overall incidence rate (alphabetical order will be used in case of equal rates).

All adverse events will be listed. Serious TEAEs will be listed, if required.

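### Protocol Section 8.3.1 collects AEs and SAEs from consent yet classes every pre-dose event as medical history, leaving unclear whether a serious reaction to a protocol-required vaccine or the Day -1 penicillin dose is an SAE

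*Protocol*

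**What the plan says.** Protocol Section 8.3.1 opens with the rule "All AEs and SAEs will be collected from the signing of the ICF until the last follow-up visit". Table 1 footnote n in the Schedule of Activities agrees: "Collection of adverse events and serious adverse events will begin after ICF signing".

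The next paragraph of 8.3.1 sets a different rule. "Medical occurrences that begin before the start of study drug and after obtaining informed consent" are the events covered, and they "will be recorded on the eCRF, and will be considered as medical history". The paragraph after that requires every SAE to reach the sponsor within 24 hours.

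Appendix 3 (Section 10.3) supplies the definitions. "An AE is any untoward medical occurrence in a patient or clinical study subject, temporally associated with the use of study drug", and "If an event is not an AE per definition above, then it cannot be a SAE even if serious conditions are met".

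SAP 4.12.1 defines a treatment-emergent AE as one that "is any adverse event that commences after the start of administration of study drug".

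**The concern.** Taken literally, the two rules in 8.3.1 cannot both apply. If everything that begins between consent and dosing is medical history, AE collection before dosing has nothing left to collect.

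This matters more here than in most single-dose studies, because the pre-dose window contains interventions that the protocol itself requires. For subjects without adequate vaccination records, Table 1 footnote e states that "MCV4 immunization will be performed at least 56 days prior to dosing on Day 1", and the serogroup B series has the same 56-day minimum with a booster at least 28 days before dosing. All subjects start oral penicillin V on the evening of Day -1 (Section 8.2.9). These are healthy volunteers with no direct benefit (Section 2.3).

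If one of them has a serious reaction in this window, the site needs to know whether to open an SAE record, assess causality and report within 24 hours. The protocol gives two answers.

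**Working it through.** No figure in the plan depends on this point, so the check compares the passages and then traces two hypothetical cases.

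**The window.** Screening runs for up to 70 days. A first vaccine dose given in the study must fall at least 56 days before Day 1, so it is given 56 to 70 days before dosing, within a slot of 70 − 56 = 14 days. The booster falls at least 28 days before Day 1 and the first penicillin dose on the evening before Day 1. All of these precede the start of study drug. The vaccines (one MCV4 and two serogroup B injections at most) go only to subjects who need them. The penicillin dose applies to all 48 planned subjects.

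**Passages that treat pre-dose AEs or SAEs as existing**
- 8.3.1, first sentence, and Table 1 footnote n: collection starts at consent.
- 5.4: any SAE is recorded for screen failures, who by definition are never assigned study drug.
- 8.3: the duty to follow up covers AEs related to study procedures, not only to study drug.
- SAP 4.16: an AE with an unknown start is assumed treatment-emergent unless it is known to have ended before first dose. That presupposes AEs that ended before dosing.

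**Passages that point the other way**
- 8.3.1, second paragraph: medical history, without exception.
- Appendix 3: an AE is tied to use of study drug, and what is not an AE cannot be an SAE.

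**Case 1: hospital admission a few days after a study-given vaccine.** Under the first group of passages this is an SAE. It gets a causality assessment, which Appendix 3 requires for every AE, and a 24-hour report. Under the second group it is medical history. The protocol requires no causality assessment for medical history, and the 24-hour rule applies only to an event already classed as an SAE. Under both, the event is entered on the eCRF.

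**Case 2: a reaction to penicillin on Day -1 that worsens after ravulizumab.**
- If the Day -1 event is medical history, the post-dose worsening is itself an AE, because Appendix 3 includes exacerbated conditions. It begins after dosing and so meets the SAP definition of a TEAE.
- If the Day -1 event is recorded as an AE, Appendix 3 has severity changes documented for that event. Onset may then stay on Day -1, and the worsening does not meet the SAP definition unless the site opens a new record.

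The TEAE gap therefore appears only once pre-dose events are recorded as AEs, which is what the repair of 8.3.1 would do. The SAP change follows from that repair and is not a separate defect.

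**The case against.** A reader might infer that a serious pre-dose reaction cannot be an SAE and would not be reported. The documents do not support this.

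- The 24-hour sentence for all SAEs comes directly after the medical-history paragraph, and Appendix 3 applies it whatever the suspected cause.
- Section 5.4 and SAP 4.16 plainly expect SAEs or AEs before dosing.
- The Appendix 3 sentence linking AE and SAE is illustrated with disease-related hospitalisation and death, not with pre-dose events.
- Section 6 defines study drug broadly enough, read literally, to include marketed products given under the protocol, which could take in the vaccines and penicillin. Table 6 and Section 8.2.9 treat study drug as something separate, so this adds ambiguity and settles nothing.

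A second inference would be that the primary safety endpoint is compromised. Events that start and end before dosing are not treatment-emergent on any reading, and Case 2 shows that post-dose worsening is counted if the medical-history rule is applied.

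Nor would the data be lost for treated subjects. The SAP lists medical history (4.8), vaccine and antibiotic prophylaxis data (4.5) and all AEs (4.12.1) by subject. Penicillin-allergic subjects are excluded, and the first penicillin dose falls on the day of admission to the unit.

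These objections limit the claim to classification, causality assessment and expedited reporting. They do not remove the conflict: they show that the documents disagree, not which passage a site would follow.

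**Conclusion.** The contradiction within 8.3.1, and between it and Table 1 footnote n, Section 5.4 and SAP 4.16, is real and should be resolved. The supportable conclusion is that SAE status, causality assessment and 24-hour reporting of a serious pre-dose event are unclear, not that such an event is excluded.

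The rule covers up to 70 days per subject. It spans the required vaccinations where given and the first antibiotic dose in all 48 planned subjects. The documents give no rate of reactions in this window, so the number of events affected cannot be estimated and no effect on TEAE incidence can be quantified.

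Subjects vaccinated in the study who then fail screening deserve particular care. SAP 4.3 keeps screen failures out of listings and tables, so for them the SAE record and its 24-hour report carry most of the weight.

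The conclusion rests on reading study drug as ravulizumab with or without rHuPH20, as Table 6 does.

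**What to change.** Reconcile Section 8.3.1, Table 1 footnote n and Appendix 3. From consent to dosing, record as non-treatment-emergent AEs or SAEs at least:
- every serious event; and
- any event linked to protocol-required vaccination, antibiotic prophylaxis or a study procedure.

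State that 24-hour reporting applies to the SAEs among them, including those in screen failures. Adjust the AE definition in Appendix 3 so that such events qualify without relying on use of study drug.

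In the SAP, list these pre-dose events separately from TEAEs. As a consequential change, define a TEAE in 4.12.1 as an event that starts, or worsens in severity, after the start of study drug, so that a pre-dose AE that worsens after dosing is still counted.

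The cost is wording in both documents, one extra listing and slightly more AE recording during screening. Sample size, visits and treatment are unaffected.
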